2.9.4.2 Vital signs

Vital sign measurements include sitting systolic and diastolic blood pressures, sitting pulse, body temperature, height and body weight.

Three sitting measurements of blood pressure (SBP and DBP) and pulse will be taken at each vital sign assessment.

For post-baseline assessments, the blood pressure and pulse values will be the average of the non-missing values of the 3 measurements. If more than one blood pressure/pulse assessment (scheduled or unscheduled) exists in a particular visit-window (as defined in Section 2.1.2.1), derivation should follow the rules as defined in Section 2.1.2.3. Derivation of baselines for blood pressure and pulse are provided in Section 2.1.1.

Height will be collected at screening visit only and will be summarized in the baseline characteristic summary only.

Analyses of vital sign measurements (excluding data collected on Day 1 protocol scheduled visit) using descriptive summary statistics (mean, median, standard deviation, min, max) for the change from baseline for each post-baseline visit-window will be performed. These descriptive summaries will be presented by vital sign parameter. Change from baseline will only be summarized for subjects with both baseline and postbaseline values and will be calculated as:

change from baseline = post-baseline value – baseline value

The number and percentage of subjects with clinically notable vital signs will be presented. For clinical notable vital signs values, refer to Table 2-14.

For vital signs data collected on Day 1 protocol scheduled visit, pre and post-injection vital signs data including temperature, pulse rate and blood pressure are collected. Change from pre-injection to post-injection in these 3 parameters will be summarized by nominal visit.

All above summaries include only data up to and including safety cut off. A listing of subjects with clinically notable vital signs values will be provided.

Table 2-14 Vital signs clinically notable values

Vital Sign	Notable criteria
Pulse (beats/min, bpm)	>120 bpm Or <50 bpm
Systolic Blood Pressure (mmHg)	≥160 mmHg Or ≤90 mmHg
Diastolic Blood Pressure	≥100 mmHg Or ≤50 mmHg
Temperature (°C)	>38.3 °C (>101 °F)
Body weight (kg)	≥7% from baseline weight

2.9.4.3 Treatment discontinuation or interruption due to lack of efficacy or tolerability

The proportion of subjects discontinuing treatment or having treatment interruption due to insufficient effectiveness (lack of efficacy) or tolerability/safety reasons will be provided. On treatment disposition CRF page, reason for discontinuation "Lack of efficacy" and "Adverse events" will be selected to provide this summary. In addition, treatment discontinuation or interruption due to lack of efficacy or safety will also be summarized by participants who have IgG < LLN at any point post-baseline vs participants who have $IgG \ge LLN$ at any point post-baseline. Same analysis will be repeated by IgM.

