6.5.3 Drug Interruptions

Conditions/events that may lead to study drug interruptions based on Investigator judgment and overall clinical assessment include:

- reported serious adverse event;
- emergency medical condition, unplanned hospitalization involving use of excluded concomitant medications;
- abnormal laboratory value(s) or abnormal test or examination result(s)

Should the subject interrupt the study drug for whatever reason, the re-start decision should be made on a case-by-case basis (refer to Section 6.7.2). Should the Investigator decide, after informing the Sponsor, to re-initiate treatment with study drug, depending on the duration of the interruption, the first dose at re-start may need to take place at the study site to ensure observation in a similar manner as on Day 1.

The reason for interruption of treatment and date of interruption should be appropriately documented in the source documents as well as in the appropriate eCRF.

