3 = severe: prevents normal activities

4 = life-threatening

- Its relationship to the study treatment.
- Its duration (start and end dates) or if the event is ongoing, an outcome of not recovered/not resolved must be reported
- Whether it constitutes a SAE (see Section 10.1.2 for definition of SAE) and which seriousness criteria have been met
- Action taken regarding with study treatment

All adverse events must be treated appropriately. Treatment may include one or more of the following:

- No action taken (e.g. further observation only)
- Drug interrupted/withdrawn
- Concomitant medication or non-drug therapy given
- Subject hospitalization/subject's hospitalization prolonged (see Section 10.1.2 for definition of SAE)
- Its outcome (not recovered/not resolved; recovered/resolved; recovered/resolved with sequelae; fatal; or unknown).

Conditions that were already present at the time of informed consent should be recorded in medical history of the subject.

Adverse events (including lab abnormalities that constitute AEs) should be described using a diagnosis whenever possible, rather than individual underlying signs and symptoms.

Adverse event monitoring should be continued for at least 100 days following the last dose of study treatment.

Once an adverse event is detected, it must be followed until its resolution or until it is judged to be permanent (e.g. continuing at the end of the study), and assessment must be made at each visit (or more frequently, if necessary) of any changes in severity, the suspected relationship to the interventions required to treat it, and the outcome.

Information about adverse drug reactions for the investigational drug (ofatumumab) can be found in the Investigator's Brochure (IB). This information will be included in the subject informed consent and should be discussed with the subject during the study as needed. Any new information regarding the safety profile of ofatumumab that is identified between IB updates will be communicated as appropriate, for example, via an Investigator Notification or an Aggregate Safety Finding. New information might require an update to the informed consent and has then to be discussed with the subject.

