1.2 Study objectives and endpoints

Table 1-1 Objectives and Endpoints

Objective(s)	Endpoint(s)		
Primary objective(s)	Endpoint(s) for primary objective(s)		
Demonstrate the effectiveness of ofatumumab 20 mg s.c. administered every 4 weeks in subjects with relapsing forms of MS who had breakthrough disease on fumarates or fingolimod	Annual relapse rate (ARR, based on confirmed relapses) measured over the 96 weeks		
Secondary objective(s)	Endpoint(s) for secondary objective(s)		
Evaluate the safety of ofatumumab 20 mg s.c. administrated every 4 weeks in subjects with relapsing forms of MS who had breakthrough disease on fumarates or fingolimod	 Proportion of subjects with adverse events, including injection related reactions Proportion of subjects with laboratory or vital signs results meeting abnormal criteria The proportion of subjects discontinuing treatment due to insufficient effectiveness (lack of efficacy) or tolerability/safety reasons 		
Exploratory objective(s)	Endpoint(s) for exploratory objective(s)		
Demonstrate effectiveness of ofatumumab 20 mg s.c. administered every 4 weeks	 Change from Baseline during the treatment period, of the following Assessments: EDSS Timed 25-Foot Walk (T25FW) Nine-Hole Peg Test (9HPT) Low Contrast Visual Acuity (LCVA) T2 lesion volume Time to 6-month Confirmed Disability Worsening (6mCDW) based on EDSS Time to a 6-month confirmed cognitive decline (6mCCD), defined as a 4-point worsening on Number of T1 Gd+ lesions per scan Number of new or enlarging T2 lesions on MRI per year (annualized T2 lesion rate) Proportion of patients without MRI activity Proportion of subjects with No Evidence of Disease Activity (NEDA-3) as per protocol defined events during a 96-week period 		
Explore patient reported outcomes in subjects treated with ofatumumab 20 mg s.c. administered every 4 weeks	Change from Baseline during the treatment period of the following Assessments: The impact of MS disease as measured by the CCI CCI CCI CCI CCI CCI CCI CCI		
Explore Neurofilament (NfL) light chain as a biomarker for MS in terms of prognosis and disease activity monitoring	Change from baseline in serum NfL light chain concentration		

Objective(s)	Endpoint(s)			
• Explore the utility of using the application	Adherence to Classessments quantified as compliance level (%), which will be measured in terms of Classessments and other assessments performed in the study CCI includes the following: CCI CCI CCI CCI CCI CCI CCI C			

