2.9.1 Adverse events (AEs)

An adverse event (AE) is any untoward medical occurrence (i.e., any unfavorable and unintended sign [including abnormal laboratory findings], symptom or disease) in a subject or clinical investigation of a subject after providing written informed consent for participation in the study. That means that a subject can report AEs before having started study medication. For reporting purposes, the main focus will be on treatment emergent adverse event (TEAE), defined as any adverse event which started on or after the day of first dose of study medication.

TEAEs and serious TEAEs up to and including safety cut-off date will be included in the analyses (see detailed explanation in Section 2.9 for safety cut off date).

AEs will be reported by primary system organ class (SOC) and preferred term according to the Medical Dictionary for Regulatory Activities (MedDRA). The MedDRA version is 27.0.

The number and percentage of subjects reporting any TEAEs (referred to as incidence of any TEAEs later) will be summarized by primary SOC and preferred term.

Separate summaries will be provided for:

- overview of TEAEs,TEAEs by primary SOC,most common TEAEs by preferred term (≥ 2%), most common TEAEs by preferred term (≥ 2%) and last prior DMT, TEAE by last prior DMT, TEAE by duration of washout
- serious TEAEs by primary SOC and preferred term, serious TEAEs by last prior DMT, serious TEAEs by duration of washout, deaths by primary SOC and preferred term,
- drug related TEAEs by primary SOC and preferred term,
- TEAEs leading to treatment interruption and permanent discontinuation of study drug by primary SOC and preferred term, TEAEs leading to treatment interruption and permanent discontinuation of study drug by last prior DMT, TEAEs leading to treatment interruption and permanent discontinuation of study drug by duration of washout, any TEAEs will also be summarized by primary SOC, preferred term, and maximum Common Terminology Criteria for Adverse Events (CTCAE) grade. Missing CTCAE grade will not be imputed.

If a subject reported more than one adverse event within the same primary system organ class, the subject will be counted only once with the maximum CTCAE grade at the system organ class level, where applicable.

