2.9.2 Deaths

Death, if meaningful number of cases reported (i.e., 5 or more cases), will be summarized by providing the number and percentage of subjects, otherwise only listing will be provided. All deaths as recorded in the final database (i.e., up to database lock) will be included.

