2.14.7 Proportion of subjects with No Evidence of Disease Activity (NEDA-3)

NEDA-3 is a composite of three related measures of disease activity: (i) no relapses; (ii) no 6-month confirmed disability worsening (6mCDW); (iii) no MRI activity (new of enlarging T2 lesions or Gd-enhancing lesion).

NEDA-3 will be set to "No" if at least one of the following conditions is met; otherwise NEDA-3 will be set to "Yes".

- 6mCDW event
- Confirmed relapse
- ≥1 Gd-enhancing T1 lesions
- ≥1 new/enlarging T2 lesions
- Discontinued from study drug due to either "death" or "lack of efficacy"

Proportions of subjects after 96 weeks that meet the criteria of NEDA-3 will be summarized descriptively by last prior DMT (fumarates vs. fingolimod), along with 95% CI.

NEDA-3 will also be summarized by year (use Day 365.25 as the cut-off of Year 1 and Year 2), as well as by year and by last prior DMT, along with corresponding 95% CI. In addition, each NEDA-3 components (Gd-enhancing T1 lesions, new and enlarging T2 lesions, MRI lesion activity, confirmed relapses, 6mCDW, discontinued from study drug due to either death or lack of efficacy) will be summarized by year.

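### SAP 2.9.4.3 announces a discontinuation-or-interruption summary but selects only two discontinuation reasons, so it captures no interruptions and probably misses deaths from a fatal on-treatment adverse event

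*SAP*

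**What the plan says.** The secondary endpoint in SAP 1.2 (Table 1-1) is: "The proportion of subjects discontinuing treatment due to insufficient effectiveness (lack of efficacy) or tolerability/safety reasons". Protocol Table 2-1 and SAP 2.8 define it the same way. All three cover discontinuation only.

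SAP 2.9.4.3, which implements the endpoint, is wider: "The proportion of subjects discontinuing treatment or having treatment interruption due to insufficient effectiveness (lack of efficacy) or tolerability/safety reasons will be provided". The rule that follows is: "On treatment disposition CRF page, reason for discontinuation 'Lack of efficacy' and 'Adverse events' will be selected to provide this summary". The section then asks for discontinuation or interruption to be split by IgG relative to the lower limit of normal, and again by IgM. It names no other data source.

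For NEDA-3, SAP 2.14.7 sets a subject to failure if, among other conditions: "Discontinued from study drug due to either 'death' or 'lack of efficacy".

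On data collection, protocol 6.5.3 requires: "The reason for interruption of treatment and date of interruption should be appropriately documented in the source documents as well as in the appropriate eCRF". Protocol 10.1.1 lists, among the items recorded for each adverse event: "Action taken regarding with study treatment".

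**The concern.** The announced summary and its derivation rule do not match, in two ways.

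First, the text promises interruptions, but the rule reads only reasons for permanent discontinuation. A programmer following it would either produce a discontinuation table under a title that mentions interruption, or devise an interruption rule that the SAP does not contain.

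Second, the rule selects two reasons, while another section of the same SAP treats death as a reason of its own. A fatal adverse event that ends treatment is plainly a safety reason for stopping, yet the rule as written would probably pass over it.

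The summary implements one of three secondary endpoints. At stake are a reproducible definition before database lock and an IgG/IgM split that shows what its title says.

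**Working it through.** The plan states no figure for this endpoint and attaches no test to it, so there is nothing to reproduce. The check sets the rule against the related sections, then sizes the effect with simple proportions.

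**Interruptions**
- Scope in SAP 2.9.4.3: discontinuation or interruption.
- Source in SAP 2.9.4.3: reason for discontinuation on the treatment disposition page.
- A subject who interrupts and resumes has no discontinuation reason to select. A subject who interrupts and later stops for one of the two reasons is already counted as a discontinuation. The rule therefore adds nobody by virtue of interruption, overall or in the IgG/IgM split.
- The split is where this matters most. Protocol 16.1.4 allows interruption at the investigator's discretion when IgG falls below 300 mg/dL, which is 300 × 10 / 1000 = 3.0 g/L. That is below the lower limit of normal of 5.65 g/L in SAP 2.9.3.1. Subjects interrupted on that ground fall in the low-IgG group, but the rule does not pick them up.
- Adverse-event records alone may not suffice as a source. Under protocol 10.1.1 a laboratory abnormality is an adverse event only if it causes signs or symptoms, is considered clinically significant, or requires therapy. The eCRF in protocol 6.5.3 is needed as well.

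**Deaths**
- Reasons selected in 2.9.4.3: lack of efficacy, adverse events.
- Reasons named in 2.14.7: death, lack of efficacy.
- If the disposition page has a separate death entry, a subject recorded under it is not selected by 2.9.4.3, even when an adverse event caused the death.

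**Size**, with N = 555 planned subjects (SAP 1.1). All event counts are assumptions; the documents give none.
- Effect per uncounted death = d / N: 1/555 = 0.18, 2/555 = 0.36 and 5/555 = 0.90 percentage points.
- With an assumed 28 subjects selected under the two reasons, the proportion is 28/555 = 5.05%. Adding 1, 2 or 5 deaths gives 29/555 = 5.23%, 30/555 = 5.41% or 33/555 = 5.95%.
- If 2%, 5% or 10% of subjects had a qualifying interruption without discontinuing, the rule would leave out about 0.02 × 555 = 11, 0.05 × 555 = 28 or 0.10 × 555 = 56 subjects.

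**The case against.** Several stronger readings are tempting, and the documents do not support them.

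- *Part of a secondary endpoint is empty.* The endpoint is discontinuation only in all three places that define it. Interruption is an addition made in 2.9.4.3. Only the handling of deaths touches the endpoint itself.
- *Interruptions cannot be found.* They are collected, in the eCRF of protocol 6.5.3 and as action taken on each adverse event. SAP 2.9.1 already plans to tabulate "TEAEs leading to treatment interruption and permanent discontinuation of study drug by primary SOC and preferred term". That table covers adverse events only and is not split by IgG or IgM, so it does not replace the summary in 2.9.4.3, but the data exist.
- *Deaths are lost from the safety report.* SAP 2.9.2 says: "All deaths as recorded in the final database (i.e., up to database lock) will be included". SAP 2.9.1 and 2.9.1.1.2 add deaths by system organ class and preferred term. They would be missing from one proportion, not from the report.
- *Every death, or every adverse event with drug withdrawn, should count.* A death may be unrelated to tolerability or safety, and NEDA-3 counts death for a different purpose. Protocol 9.1.1 records the primary reason for stopping, and basing the endpoint on it is a legitimate rule. The table of adverse events leading to discontinuation answers a different question and need not agree with it.

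The best remaining objection is that the CRF is not among the documents. A site might record a fatal adverse event under 'Adverse events', in which case no such death is missed. That stands as a limit on the second half of the point, and is also a reason to state the rule. It does not affect the first half: a discontinuation reason cannot identify an interruption, however the page is laid out.

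**Conclusion.** The point holds in two parts of unequal certainty. That the rule in 2.9.4.3 cannot deliver the interruption part or its IgG/IgM split follows directly from the SAP text. That it omits a subject whose disposition reason is death after a fatal on-treatment adverse event is probable. It rests on the inference from 2.14.7 that death is a separate entry on the disposition page.

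The effect of deaths on the proportion is small, at 0.18 percentage points each on 555 subjects. The number of interruptions left out is unknown; the 11 to 56 above depends wholly on the assumed 2% to 10%. The endpoint is descriptive, so no hypothesis test or primary result is affected. The change is still worth making, because the stated rule does not produce the stated summary and the data needed are already collected.

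**What to change.** Replace the derivation sentence in SAP 2.9.4.3 with three rules.

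1. Report the secondary endpoint, discontinuation only, on its own row. Count subjects whose treatment disposition reason is 'Lack of efficacy' or 'Adverse events', plus those with reason 'Death' where the death resulted from a treatment-emergent adverse event. Check the disposition page first; if fatal adverse events are already entered under 'Adverse events', say so.
2. Report interruptions on a separate row, taken from the eCRF that holds the reason and date of interruption (protocol 6.5.3) and from adverse-event records whose action taken is drug interrupted.
3. Apply both rules to the IgG and IgM split.

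The primary-reason basis for discontinuation can stay. Add a footnote that the count can differ from the table of adverse events leading to discontinuation in SAP 2.9.1.

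The cost is a short SAP edit and minor programming on data already collected. The reported discontinuation proportion may be slightly higher.

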Subjects who prematurely discontinue the study for any reason should be scheduled for the EOS visit as soon as possible and then enter the Safety Follow-up period according to the schedule in Table 8-2. At this final visit, all dispensed investigational product should be reconciled, and the adverse events and concomitant medications recorded on the CRF.

 Table 8-1
 Assessment Schedule, Treatment

Period	Scre	ening	Treatment												
Visit Name	Screening	Baseline	Visit 12	Visit 2 (Remote contact Visit) ³	Visit 3 Week 2 ²⁴	Visit 4 Week 4	Visit 5 Week 8 ²⁴	Visit 6 Week 12 ²⁴	Visit 7 Week 24	Visit 8 Week 36 ²⁴	Visit 9 Week 48	Visit 10 Week 60 ²⁴	Visit 11 Week 72	Visit 12 Week 84 ²⁴	EOS/Visit 13 Week 96 ⁴
Visit Numbers ¹	1	20	100	110	120	130	140	150	160	170	180	190	200	210	220
Days	-60 to -8	-7 to 1 (Prior to 1 st dose/visit 1 start)	1	7 ±1	14 ±1	28 ±1	56 ±7	84 ±7	168 ±14	252 ±14	336 ±14	420 ±14	504 ±14	588 ±14	672 ±14
Informed Consents ²⁴	Х														
Demography, Height	Х														
Medical History	Х														
MS History/Treatments ⁵	Х														
Inclusion / Exclusion criteria	Х	Х													
Patient Training ^{6,7}		Х	Χ												
Drug dispensation			Х		Х	Х	Х	Х	Х	Х	Х	Х	Х	X ²⁸	
Site contact with subjects ⁸				Х					Мс	onthly bet	ween so	heduled	visits		
MS Relapse	X ²⁷	Х	Х	Х	Х	Х	Х	Х	Х	Х	Х	Х	Х	Х	Х
EDSS	Х	X ²⁰							Х		Х		Х		Х
MRI ⁹	X ¹⁰								Х		Х				X ¹¹
Office examinations 12			X ¹³						Х		Х		Х		Х
CCI															
LCVA			X ¹³								Х				Х
PROs ¹⁴			X 13			Х			Х		Х		Х		Х
CCI			X 13								Х				Х

Period	Scre	ening						Tre	eatment						
Visit Name	Screening	Baseline	Visit 12	Visit 2 (Remote contact Visit) ³	Visit 3 Week 2 ²⁴	Visit 4 Week 4	Visit 5 Week 8 ²⁴		Visit 7 Week 24	Visit 8 Week 36 ²⁴	Visit 9 Week 48	Visit 10 Week 60 ²⁴	Visit 11 Week 72	Visit 12 Week 84 ²⁴	EOS/Visit 13 Week 96 ⁴
Visit Numbers ¹	1	20	100	110	120	130	140	150	160	170	180	190	200	210	220
Days	-60 to -8	-7 to 1 (Prior to 1 st dose/visit 1 start)	1	7 ±1	14 ±1	28 ±1	56 ±7	84 ±7	168 ±14	252 ±14	336 ±14	420 ±14	504 ±14	588 ±14	672 ±14
CCI		X ²⁵	Х		Х	×	Х	X	×	х	Х	X	х	Х	×
CCI review ¹⁶		X ²⁵	Х		Х	Χ	Х	Χ	Х	Х	Χ	Χ	Х	Х	Х
Vital Signs	Х	X	X ¹⁷			X			Х		Χ		Х		Х
Physical Exam (including weight) ⁶	Х					Х			X		Х		Х		Х
Electrocardiogram (ECG)	Х														Х
Biomarker sampling ^{18,19}	Х					Х		Χ	Х	Х	Х	Х	Х	Х	Х
Total IgG, IgM levels	Х					Х			Х		Χ		Х		Х
Routine lab samples including urine	Х	X ²⁰				Х		Х	×		Х		Х		Х
Sample for CD19+ B-cells (all sites)		X				Х			X		Х		Х		Х

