- In case the investigator deems the benefit-risk of continuing study treatment to be unfavorable or if the subject does not wish to continue study treatment, the subject will be discontinued from the study and will enter the Safety Follow-up period (Table 8-2). The investigator will be notified by the Sponsor when a subject meets the criterion for 6mCDW.

If discontinuation of study drug occurs, the investigator should make a reasonable effort to understand the primary reason for the subject's premature discontinuation of study drug and record this information.

Subjects who discontinue study drug or who decide they do not wish to participate in the study further should NOT be considered withdrawn from the study UNLESS they withdraw their consent (see Section 9.1.2). Subjects that discontinue treatment should complete the EOS visit and move to the Safety Follow-up as per Table 8-2. If they fail to return for these assessments for unknown reasons, every effort (e.g. telephone, e-mail, letter) should be made to contact the subject/pre-designated contact as specified in Section 9.1.3. This contact should preferably be done according to the study visit schedule.

If the subject cannot or is unwilling to attend any visit(s), the site staff should maintain regular contact with the subject, or with a person pre-designated by the subject. This contact should preferably be done according to the study visit schedule for up to 6 months post last study drug administration.

After study drug discontinuation, at a minimum, in abbreviated visits, the following data should be collected at clinic visits or via telephone/email contact:

- New / concomitant treatments
- Adverse Events / Serious Adverse Events

The investigator must also contact the IRT to register the subject's discontinuation from study drug.

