12.5.2 Safety endpoints

For all safety analyses, the safety set will be used. All listings and tables will be presented for all subjects in the safety set. Unless explicitly otherwise stated, only data up to and including the safety cutoff of 100 days after permanent study drug discontinuation will be included in the analysis and data beyond this time point for a patient will be excluded from safety analysis. In addition, a separate summary for death including on treatment and post treatment deaths will be provided. In particular, summary tables for adverse events (AEs) will summarize only ontreatment events, which started or worsened during the on-treatment period (treatment-emergent AEs).

The on-treatment period for safety analysis lasts from the date of first administration of study drug to 100 days after the date of the last actual administration of study drug.

The sensitivity analysis for safety endpoints based on modalities for data collection (on-site or remotely) and based on pandemic phase indicator may be performed if there is sufficient data.

Adverse events

All information obtained on adverse events will be displayed. The number (and proportion) of subjects with AEs of special interest/related to identified and potential risks will be summarized.

A subject with multiple AEs within a primary system organ class is only counted once towards the total of the primary system organ class. Summary tables for AEs will include only AEs that started or worsened during the on-treatment period, the *treatment-emergent* AEs.

The incidence of treatment-emergent AEs (new or worsening from baseline) will be summarized by system organ class and/or preferred term, severity (based on CTCAE grades), type of AE, relation to study drug.

Adverse events, Serious AEs and adverse events of special interest (AESI) during the ontreatment period will be tabulated.

All deaths (on-treatment and post-treatment) will be summarized. All AEs, death and serious AEs (including those from the pre and post-treatment periods) will be listed and those collected during the pre-treatment and post-treatment period will be flagged.

Vital signs

Vital signs data may be listed by subject, and visit/time and if ranges are available, abnormalities will be flagged. Summary statistics will be provided by visit/time.

Clinical laboratory evaluations

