2.8 Analysis of secondary objective(s)

The secondary objective is to evaluate the safety of ofatumumab 20 mg s.c. administrated every 4 weeks in subjects with relapsing forms of MS who had breakthrough disease on fumarates or fingolimod.

Below are the secondary endpoints defined to evaluate secondary objective.

- Proportion of subjects with adverse events, including injection related reactions
- Proportion of subjects with laboratory or vital signs results meeting abnormal criteria
- The proportion of subjects discontinuing treatment due to insufficient effectiveness (lack of efficacy) or tolerability/safety reasons

Since these objectives are related to safety, details on analysis is provided in safety Section 2.9.

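### SAP 2.9.4.3 groups discontinuation by low IgG or IgM at any time after baseline, so with no true link discontinuation looks lower in subjects with low immunoglobulin

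*SAP*

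**What the plan says.** The proportion of subjects who stop drug for lack of efficacy or for tolerability or safety reasons is a secondary endpoint (SAP 2.8: "The proportion of subjects discontinuing treatment due to insufficient effectiveness (lack of efficacy) or tolerability/safety reasons"). SAP 2.9.4.3 adds a breakdown by immunoglobulin: treatment discontinuation or interruption for lack of efficacy or safety "will also be summarized by participants who have IgG < LLN at any point post-baseline vs participants who have" IgG at or above LLN at any such point. It then adds "Same analysis will be repeated by IgM". The visible text sets no landmark, no time-dependent status, no person-time rate, and no rule that the low value must come before the event.

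Protocol Table 8-1 (row "Total IgG, IgM levels") samples at screening, Weeks 4, 24, 48 and 72, and EOS/Week 96. A subject who stops leaves that schedule (Protocol 9.1.1): "Subjects that discontinue treatment should complete the EOS visit and move to the Safety Follow-up as per Table 8-2". Table 8-2 samples again at EOS + 3 and + 6 months, then every 3 months if needed. For safety analyses in general, Protocol 12.5.2 says that "only data up to and including the safety cutoff of 100 days after permanent study drug discontinuation will be included". The SAP's own cut-off sentence is not fully legible in the public copy, so it is unclear how many follow-up samples count.

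**The concern.** The grouping variable is measured over the same period that the outcome cuts short. A completer has five scheduled chances after baseline to show a low value. A subject who stops at Week 10 has the Week 4 sample, an EOS sample and perhaps some follow-up samples. To be classed low on a later on-treatment value, a subject must first have stayed on drug until that value. This is immortal-time bias. A value that first turns low after the stop also puts the subject in the low group, although it cannot have led to the stop.

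In the visible text this is the only comparison linking low immunoglobulin to stopping or interrupting drug, and Protocol 16.1.4 recognises low IgG as a possible reason to interrupt. A table tilted towards fewer discontinuations in low-Ig subjects could be read as reassurance that the data do not give.

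**Working it through.** The documents state no figure for this summary, so there is none to reproduce. The check asks what the table would show if low Ig and stopping were unrelated (true ratio 1).

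**Inputs from the documents.** Treatment lasts 96 weeks, T = 672 days (Protocol 6.1.4). Sampling times are as in Tables 8-1 and 8-2. IgG LLN is 5.65 g/L (SAP 2.9.3.1), and entry allows IgG from 500 mg/dL = 5.0 g/L (Protocol 5.2, criterion 17).

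**Assumed, not in the documents.** A share s = 5-10% stops, uniformly over T. A share p = 5-30% would be low by Week 96, at a constant onset rate, and stays low. Nobody is low at entry. Discontinuers' last counted sample falls d days after stopping. Groups are ever-low against never-low.

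**Formulas.** Let Λ = −ln(1 − p).
- Ever-low among completers: p.
- Ever-low among discontinuers: q = 1 − e^(−Λd/T) × (1 − e^(−Λ))/Λ.
- Discontinuation in ever-low: A = sq / [sq + (1 − s)p].
- Discontinuation in never-low: B = s(1 − q) / [s(1 − q) + (1 − s)(1 − p)].

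**One case in full:** s = 0.10, p = 0.10, Λ = 0.1054.
- d = 0 (EOS sample counted): q = 1 − 0.10/0.1054 = 0.0509. A = 0.00509/(0.00509 + 0.09) = 5.35%. B = 0.0949/(0.0949 + 0.81) = 10.49%. Ratio 0.51.
- d = 90 (about Safety Follow-up Visit 1): q = 0.0642, A = 6.66%, B = 10.36%, ratio 0.64.
- d = 180 (about Visit 2): q = 0.0773, A = 7.91%, B = 10.23%, ratio 0.77.

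**Over the assumed ranges** (simulation; the formulas agree to within 0.01):

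| Samples counted for discontinuers | Ratio, discontinuation |
|---|---|
| through EOS | 0.46-0.52 |
| to about 3 months after EOS | 0.59-0.65 |
| to 6 months after EOS | 0.73-0.79 |

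**Interruption.** A subject who interrupts and resumes keeps the full Ig schedule. Simulated under the null, interruption alone gives a ratio of 1.01-1.06. It is slightly above 1 because longer time on drug gives more chance both to interrupt and to be found low.

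**Combined outcome**, with a share r interrupting (assumed 5-30%): risk is roughly 1 − (1 − A)(1 − r), and likewise for B.
- r = 5%, d = 0: 1 − 0.9465 × 0.95 = 10.1% against 1 − 0.8951 × 0.95 = 15.0%; ratio 0.67.
- r = 30%, d = 90: 1 − 0.9334 × 0.70 = 34.7% against 1 − 0.8964 × 0.70 = 37.3%; ratio 0.93.

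Simulation at s = p = 10% gives 0.68-0.93, the same within rounding.

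**What moves the discontinuation ratio.**
- 5% already low at entry (s = p = 0.10, d = 0): completers 0.05 + 0.95 × 0.10 = 0.145; q = 0.05 + 0.95 × 0.0509 = 0.0983; A = 7.0%, B = 10.5%, ratio 0.67.
- Front-loaded Ig decline (Weibull shape 0.5): 0.66-0.70 through EOS, 0.77-0.79 to 100 days, 0.86-0.88 to 6 months.
- Stopping weighted to the early months (10% stop, 20% low): 0.35-0.65, a larger bias.
- Literal SAP wording (any low against any normal value, with about 95% of low subjects in both groups): 0.55-0.82.

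**After the fix**, a person-time rate ratio with time-dependent status is 1.00-1.03 under the null.

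**The case against.** The strongest reply is that the planned outcome is discontinuation or interruption together. Interruption does not shorten Ig observation, so a ratio near 0.5 describes only one component. This stands, and the combined range of about 0.68-0.93 is the right one for the table as written.

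Next, discontinuers are still sampled at EOS and in follow-up, and some subjects may enter below LLN. Both points stand. They shrink the bias, but no scenario tried for discontinuation or the combined outcome reached 1.

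Third, this is one descriptive table with no test. TEAEs leading to interruption or discontinuation are tabulated elsewhere (SAP 2.9.1), as are low Ig levels by visit (SAP 2.9.3.1). That limits the consequence. Neither of those tables relates Ig status to stopping in the visible text, so neither corrects this one.

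A reader might infer that interruption is biased in the same way, that the planned table will show roughly half the events in low-Ig subjects, or that a real harm will be hidden. The documents support none of these. Interrupted subjects stay on the schedule, the halving applies only to discontinuation with sampling through EOS, and the documents give no evidence of a harm to hide.

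**Conclusion.** The point holds for discontinuation and, diluted, for the combined outcome. It does not hold for interruption alone. The direction follows from the grouping rule and the sampling schedule. The size depends on rates that the documents do not give and on a safety cut-off that is only partly visible in the SAP. Making the groups non-overlapping would not cure it, because the ever-low against never-low split was the one tested. The primary endpoint is not affected. The change is worth making because the table addresses a safety question about a B-cell depleting drug and leans towards reassurance, but it is a correction to one descriptive summary.

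**What to change.** In SAP 2.9.4.3, define low Ig as a time-dependent state. On-drug time counts as not low until the first post-baseline sample below LLN, and as low after it. Assign each event to the state at its date, and do not use samples taken after the event to classify it. Report events per 100 patient-years in each state, separately for discontinuation and interruption and separately for IgG and IgM. This also makes the groups mutually exclusive.

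The cost is SAP wording and minor programming with dates already collected, and a percentage table becomes a rate table. There is one real loss. After Week 4 the samples are 20-24 weeks apart, so a fall in Ig between visits shortly before stopping is counted as not low. A listing of discontinuers whose first low value is at EOS would show those cases.
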